#### 4.8 Number of study drug administration days

The number of days that the study drug is taken (administered) is defined by the following formula.

Number of MT-6548 administration days (days) = Period of study drug administration – Number of days of no study drug administration other than drug interruptions – Number of days of drug interruptions

## 4.9 Study drug compliance rate

Study drug compliance rate (%) = Number of days of study drug use / (Period of study drug use – Number of days of drug interruptions) × 100

However, if the compliance rate exceeds 100%, it should be 100%.

## 4.10 Mean daily dose

Mean daily dose of MT-6548 during each scheduled study visit period\* = Daily dose based on the physician's prescription × Period of administration (days)\*3 of the corresponding dose\*2 between the scheduled study visits\* / Period between the scheduled study visits (days)\*4

\*: For each period between the scheduled study visits, the actual study visit dates will not be considered, and this variable should be fixed as follows:

- ✓ The first day of the treatment period to Week 2 of the treatment period: The first day of the treatment period (Day 1) to Day 14
- ✓ Week 2 of the treatment period to Week 4 of the treatment period: Day 15 to Day 28
- ✓ The same shall apply thereafter, and the final period between the scheduled study visits should be Week 20 to Week 24 of the treatment period: Day 141 to a blood sampling day for hematological tests at Week 24 of the treatment period.

However, for subjects who discontinued their treatment, the final period between the scheduled study visits should be up to the day before discontinuation.

\*: If there are multiple applicable doses, the sum of the calculated values for each dose should be used.

\*: The number of days without drug administration other than drug interruption should not be excluded from the "period of administration (days)".

\*: 14 days up to Week 12 of the treatment period and 28 days after Week 12 of the treatment period. However, for subjects who discontinued their treatment, the final period between the scheduled study visits (days) should be the actual number of days until the day before discontinuation.

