### 8.3 Dosage and administration

- (1) Initial dosage levels

- 1) Initial dosage for correction cohort  
Single daily dose of 300 mg (2 tablets)
- 2) Initial dosage for conversion cohort  
Single daily dose of 300 mg (2 tablets)

- (2) Maintenance dosage and dosage adjustments

Maintenance dosage is 150 to 600 mg once daily and adjusted according to the dosage adjustment guideline below.

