## 8.4 Treatment period

From the first day of the treatment period to the day prior to Week 24 of the treatment period.

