**8.5.4.3 Multicenter trial**

For FAS, the following analysis should be conducted for each following endpoint for each site. Descriptive statistics of Hb values should be calculated at Week 24 of the treatment period (imputed by the LOCF method).

Descriptive statistics should be calculated for the mean dose of the study drug at Week 20 to Week 24 of the treatment period. No analysis will be performed for each patient cohort.

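### For completers, the Week 20–24 mean daily dose counts drug up to the actual Week 24 visit but divides by a fixed 28 days, so a constant dose can be reported up to 25% too low or too high

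*SAP*

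**What the plan says.** SAP 4.10 opens with a general rule for the periods between visits: "the actual study visit dates will not be considered, and this variable should be fixed as follows". The first block is "The first day of the treatment period (Day 1) to Day 14", and the later ones follow the same pattern. The last block departs from the rule. For completers it is "Day 141 to a blood sampling day for hematological tests at Week 24 of the treatment period", which is an actual date.

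Footnote 4 gives the divisor as "14 days up to Week 12 of the treatment period and 28 days after Week 12 of the treatment period". Its only exception is for discontinued subjects, for whom "the final period between the scheduled study visits (days) should be the actual number of days until the day before discontinuation".

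Protocol 8.4 defines the dosing period as "From the first day of the treatment period to the day prior to Week 24 of the treatment period". Protocol Table 9.1-1 puts Week 24 at Day 168 (first day = Day 0), with a permitted range of Day 161 to 175. Protocol 8.3 gives the dose range: "Maintenance dosage is 150 to 600 mg once daily".

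The Week 20–24 value is used in several outputs. SAP 8.5.2(4) summarises mean daily dose by visit period, overall and by previous ESA. SAP 8.5.4.3 asks for it by site: "Descriptive statistics should be calculated for the mean dose of the study drug at Week 20 to Week 24 of the treatment period". SAP 8.5.4.4 makes it the second endpoint of the subgroup table.

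**The concern.** A mean daily dose is a total divided by the number of days over which that total was accumulated. In every earlier block both parts refer to the same fixed days. In the final block for completers the total follows the visit date and the divisor does not. A subject who never changes dose is therefore reported as having a lower dose after an early visit and a higher dose after a late one, with both visits inside the permitted window.

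This is the last on-treatment dose summary in the trial and the only study-drug dose measure in the by-site analysis and the subgroup table. With a target of 40 subjects across several centres, many of those cells will be small. If visit timing happens to differ between cells, the dose will appear to differ too. Even where early and late visits balance, the mismatch adds spread to the SD, the range and the confidence interval. The last point of the dose time-course figure would also be computed differently from the points before it.

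**Working it through.** **Inputs**
- Final block starts on SAP Day 141 and the divisor is 28 (SAP 4.10).
- Week 24 reference Day 168, permitted Day 161 to 175, first day = Day 0 (Protocol Table 9.1-1).
- The SAP calls the first day Day 1, so SAP day = protocol day + 1.
- Last dose is the day before Week 24 (Protocol 8.4).

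**1. Reproduce the plan's divisors.** Block length = last day − first day + 1.
- Days 1–14: 14
- Days 85–112, 113–140 and 141–168: 28 each
- Six blocks of 14 and three of 28 give 84 + 84 = 168 days. This equals the SAP 4.7 duration for a completer seen on the reference day (168 − 0).

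So 28 is correct for the last block when the visit is on the reference day, and only then.

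**2. Days counted when the visit moves.** A visit on protocol Day *d* is SAP Day *d* + 1, so the last dosing day is SAP Day *d*. Days counted = *d* − 141 + 1 = *d* − 140.

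**3. Reported dose** = true constant dose × (*d* − 140) / 28.

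| Week 24 visit (protocol day) | Days counted | Factor | 300 mg reported as | 600 mg reported as |
|---|---|---|---|---|
| 161 (7 early) | 21 | 0.750 | 225.0 mg | 450.0 mg |
| 165 (3 early) | 25 | 0.893 | 267.9 mg | 535.7 mg |
| 168 (on time) | 28 | 1.000 | 300.0 mg | 600.0 mg |
| 171 (3 late) | 31 | 1.107 | 332.1 mg | 664.3 mg |
| 175 (7 late) | 35 | 1.250 | 375.0 mg | 750.0 mg |

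**4. When the 600 mg maximum is exceeded.** At the late edge, any true mean dose above 600 × 28/35 = 480 mg is reported above 600 mg.

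**5. Alternative day count.** Read literally, the SAP window includes the sampling day. The days counted are then 22, 29 and 36, and the factors are 22/28 = 0.786, 29/28 = 1.036 and 36/28 = 1.286. The error runs from −21.4% to +28.6%, and even an on-time visit is 3.6% too high (600 mg reported as 621.4 mg).

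**6. Matched days.** With the divisor equal to the days counted, 600 × 21/21 = 600 × 35/35 = 600 mg. A constant dose is returned exactly for any visit day.

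**The case against.** The strongest reply is that the SAP also supports a reading with no error. The general rule in 4.10 sets actual visit dates aside, and SAP 8.5.2(4) ends each period on the day before the next scheduled visit. On that basis Week 20–24 is Days 141–168, and 28 is right. The fault would then lie in the reference to the sampling day, not in the divisor. This is a fair description of the conflict, but it does not remove it. The specific instruction for the last block names the sampling day, a programmer following it gets the mismatch, and the errata revise the Week 24 end date in 4.6 without touching 4.10.

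The second reply concerns size. The 25% figure applies to one subject at the edge of the window, and much of the error could cancel in the overall mean. Suppose, as an assumption not found in the documents, that visits are spread evenly over the 15 days of the window. The SD of the shift is √((15² − 1)/12) = 4.32 days, or 4.32/28 = 15.4% of dose per subject. The standard error over 40 subjects is 15.4%/√40 = 2.4%. That point stands for the overall mean under symmetric timing. It does not help the SD, the range, or small site and subgroup cells. A false difference between cells does require timing to differ between them, and the documents cannot show whether it does.

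Third, the endpoint is descriptive and not primary, and the earlier periods and the prescribed-dose distribution up to Week 20 are sound. This is correct and limits the importance of the point.

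**Conclusion.** The concern holds. As written, SAP 4.10 uses different lengths of time above and below the line for completers in the final period. For a subject on a constant dose, the error ranges from −25% to +25% across the permitted Week 24 window if dosing ends the day before the visit, and from −21.4% to +28.6% if the sampling day is counted. A visit three days off gives about 11% on the first count. The average error in the trial cannot be derived, because it depends on visit dates that the documents do not give.

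The effect is confined to the Week 20–24 mean daily dose and the tables and figures built on it. Haemoglobin endpoints, earlier dose periods and discontinued subjects are not affected. The text should be corrected, but the point does not threaten the trial's main conclusions.

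**What to change.** Choose one definition of the final window in SAP 4.10 and use it for both parts of the ratio.

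- **Preferred:** for completers, count from Day 141 to the day before Week 24 sampling, and in footnote 4 divide by that actual number of days. This extends the rule already used for discontinued subjects. It changes the stated end of the window as well as the divisor, so both lines need editing.
- **Alternative:** end the window at Day 168 for both parts. A subject seen before the reference day still needs the actual number of days as divisor, because a cap alone does not correct early visits.

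Make the period description in SAP 8.5.2(4) agree with the choice. SAP 4.14 (iron dose) uses the same final window without stating a completers' divisor, so state the matching rule there too.

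The cost is one line of SAP text and program for the dose variable. No new data are needed and trial conduct does not change.

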## 4.11 Cumulative dosage

The cumulative dosage of the study drug is defined by the following formula.

Cumulative dosage of MT-6548 = 150 mg × Days of 150 mg administration + 300 mg × Days of 300 mg administration + 450 mg × Days of 450 mg administration + 600 mg × Days of 600 mg administration

Number of administration days of X mg\* = Day when dose was changed from X mg – First day of X mg administration (not excluding the number of days of no drug administration)

If there are multiple applicable periods, the sum of them should be used.

\*: X indicates each dosage of MT-6548.

## 4.12 Adverse drug reactions

Adverse events for which a causal relationship to the study drug was evaluated as “reasonable possibility” are defined as adverse drug reactions.

## 4.13 Hb value increase rate

The Hb value increase rate is defined as the rate calculated using the following method.

✓ Hb value increase rate (g/dL/week):

$(\text{Hb value at Week 4 of the treatment period} - \text{Hb value at the start of the treatment period}) / ((\text{Hb value measurement day at Week 4 of the treatment period} - \text{Hb value measurement day at the start of the treatment period}) / 7)$

✓ Hb value increase rate (regression) (g/dL/week):

The slope of the regression line calculated based on the Hb values measured from the first day of the treatment period to Week 6 of the treatment period and the measurement day (weeks from the first day of the treatment period) is defined as the Hb value increase rate (regression). Subjects without data at the first day and Week 6 of the treatment period should be excluded from the tabulation. The number of weeks from the first day of the treatment period used to obtain the regression line is defined by the following formula.

First day of the treatment period: 0

Week 2 of the treatment period:  $(\text{Measurement day at Week 2 of the treatment period} - \text{the first day of the treatment period}) / 7$

Week 4 of the treatment period:  $(\text{Measurement day at Week 4 of the treatment period} - \text{the first day of the treatment period}) / 7$

Week 6 of the treatment period:  $(\text{Measurement day at Week 6 of the treatment period} - \text{the first day of the treatment period}) / 7$

Unscheduled study visit from the first day of the treatment period to Week 6 of the treatment period:  $(\text{Day of unscheduled study visit} - \text{the first day of the treatment period}) / 7$

## 4.14 Iron supplement dosage

The dose of iron supplements is defined by the following formula.

Mean monthly dose of iron supplements during the screening period\* and each scheduled study visit period (tabulation period of iron supplements) =  $(\text{Daily dose based on the physician's prescription} \times \text{Period of administration [days] of the corresponding dose}^3 \text{ during the tabulation period of iron supplements}) / \text{Tabulation period of iron supplements (days)}^4 \times 30.4375^5$

\*: The number of days of the screening period is “First day of the treatment period – First day of the screening period”.

\*2: For each period between the scheduled study visits, the actual study visit dates are not considered, and this tabulation is fixed as follows:

- ✓ The first day of the treatment period to Week 2 of the treatment period: The first day of the treatment period (Day 1) to Day 14
- ✓ Week 2 of the treatment period to Week 4 of the treatment period: Day 15 to Day 28
- ✓ The same shall apply thereafter, and the final period between the scheduled study visits should be Week 20 to Week 24 of the treatment period: Day 141 to a blood sampling day for hematological tests at Week 24 of the treatment period. However, for subjects who discontinued their treatment, the final period between the scheduled study visits should be up to the day before discontinuation.

\*3: If there are multiple applicable doses, the sum of the calculated values for each dose should be used.

\*4: For subjects who discontinued their treatment, the final period between the scheduled study visits (days) should be the actual number of days until the day before discontinuation.

\*5: In this tabulation, 1 month is counted as 30.4375 days ( $365.25/12 = 30.4375$ ).

#### 4.15 QOL (EQ-5D-5L) index value

Responses to five questions (mobility [Mo], self care [Sc], usual activities [Ua], pain / discomfort [Pd], anxiety / depression [Ad] in 5 levels (level 1 is healthy and the level goes up to 5, and the health status decreases with increases in level) are converted into index values. The index value is calculated using the Japanese EQ-5D-5L conversion table (Table 4.14.1) [1].

- (1) The responses to questions from Mo to Ad should be arranged side by side into five numbers (hereinafter, health state). The health state can exist from “11111” to “55555”.
- (2) If all five responses are 1, i.e. the health state is “11111”, the index value is 1. If the health state is other than “11111”, “Constant term: -0.060924” in Table 4.14.1 and the estimated value of the coefficient for each level of the response to each question are used to obtain the index value using the following formula The index value of the subject should be missing if one of the 5 questions has not been answered.

Index value = 1 + “Estimate of the constant term” + “Sum of ‘estimated coefficients corresponding to levels of responses other than 1”

Table 4.15.1 Japanese EQ-5D-5L conversion table

Item	Level	Estimate	Standard error	p value
Constant term		-0.060924	0.013625	<0.0001
Mo	2	-0.063865	0.008996	<0.0001
	3	-0.112618	0.009287	<0.0001
	4	-0.179043	0.010231	<0.0001
	5	-0.242916	0.009425	<0.0001
Sc	2	-0.043632	0.008931	<0.0001
	3	-0.076660	0.009972	<0.0001
	4	-0.124265	0.010129	<0.0001
	5	-0.159659	0.008924	<0.0001
Ua	2	-0.050407	0.009205	<0.0001
	3	-0.091131	0.010005	<0.0001
	4	-0.147929	0.009744	<0.0001
	5	-0.174786	0.009115	<0.0001
Pd	2	-0.044545	0.008354	<0.0001
	3	-0.068178	0.010052	<0.0001
	4	-0.131436	0.008985	<0.0001
	5	-0.191203	0.009604	<0.0001
Ad	2	-0.071779	0.009701	<0.0001
	3	-0.110496	0.010863	<0.0001
	4	-0.168171	0.009850	<0.0001
	5	-0.195961	0.009164	<0.0001

Mo: mobility, Sc: self care, Ua: usual activities, Pd: pain / discomfort, Ad: anxiety / depression

#### 4.16 QOL (KDQOL) scoring

Step 1 (See Table 4.15.1): The appropriate score is converted from the response choices for each item number in Table 7.5.3.2 for each subject.

Table 4.16.1 Step 1 in KDQOL scoring 

Item number	Response choices	Score
Question 4 A–D Question 5 A–C, Question 21	1	0
	2	100
Question 3 A–J	1	0
	2	50
	3	100
Question 19 A, B	1	0
	2	33.33
	3	66.66
	4	100
Question 10 Question 11 A, C Question 12 A–D	1	0
	2	25
	3	50
	4	75
	5	100
Question 9 B, C, F, G, I Question 18 B	1	0
	2	20
	3	40
	4	60
	5	80
	6	100
Question 20	1	100
	2	0
Question 1, Question 2, Question 6, Question 8 Question 11 B, D, Question 14 A–M, Question 15 A–H, Question 16 A, B Question 24 A, B	1	100
	2	75
	3	50
	4	25
	5	0
Question 7 Question 9 A, D, E, H Question 13 A–F Question 18 A, C	1	100
	2	80
	3	60
	4	40
	5	20
	6	0
Question 23	1	100
	2	83.33
	3	66.66
	4	50
	5	33.33
	6	16.66
	7	0

Step 2 (See Table 4.15.2): The mean of the scores calculated at Step 1 in the item numbers in the right column of Table 4.15.2 should be calculated for each subject by subscale. For questions 17 and 22, the scores obtained are multiplied by 10 to convert the values from 0 to 100. The mean value should be the score for each subject by subscale. If at least one question constituting the subscale is answered, the subscale should be tabulated without missing. If “No” is chosen in question 16, the question 16 should be treated as missing.

Table 4.16.2 Step 2 in KDQOL scoring 

- Each item score should be averaged to calculate each subscale score

Subscale	Number of items	After scoring according to Table 4-1, the mean of the items included in each subscale should be calculated.
Kidney disease-specific scale		
Symptoms	12	Questions 14 A–K, L (M)*
Effects of kidney disease on daily life	8	Question 15 A–H
Burden due to kidney disease	4	Question 12 A–D
Working status	2	Question 20, Question 21
Cognitive function	3	Question 13 B, D, F
Relationship with people	3	Question 13 A, C, F
Sexual function	2	Question 16 A, B
Sleep	4	Question 17, Question 18 A–C
Social support	2	Question 19 A, B
Encouragement from dialysis staff	2	Question 24 A, B
Patient satisfaction with dialysis care	1	Question 23
Comprehensive scale (SF-36)		
Physical functioning	10	Question 3 A–J
Daily role functioning (physical)	4	Question 4 A–D
Bodily pain	2	Question 7, Question 8
General health	5	Question 1, Question 11 A–D
Vitality	4	Question 9 A, E, G, I
Social functioning	2	Question 6, Question 10
Daily role functioning (emotional)	3	Question 5 A–C
Mental health	5	Question 9 B, C, D, F, H

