##### 2) KDQOL

Descriptive statistics of KDQOL should be calculated by subscale (Section 4.16 [Table 4.16.2] "subscale") for measured values and changes from the first day of the treatment period at each evaluation time point. Scores by subscale should be calculated using a scoring method (Section 4.16). A paired t-test should be performed for before and after comparison of changes in KDQOL from the first day of the treatment period.

LSMean, its standard errors, and 2-sided 95% CI should be calculated and shown for the change in KDQOL from the first day of the treatment period to each evaluation time point using the MMRM model (with compound symmetry [CS] for a covariance matrix within subject variance).

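### SAP Table 4.16.2 uses KDQOL item 13F in two subscales and item 13E in none, so at least one row is wrong, most likely Relationship with people

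*SAP*

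**What the plan says.** SAP Section 4.16 scores the KDQOL in two steps.

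- **Step 1 (Table 4.16.1)** converts answers to item scores. "Question 13 A–F" appears in the block where answer 1 scores 100, each further answer scores 20 less, and answer 6 scores 0.
- **Step 2 (Table 4.16.2)** assigns items to subscales: "Each item score should be averaged to calculate each subscale score". Cognitive function is given three items, "Question 13 B, D, F". Relationship with people is given three items, "Question 13 A, C, F".
- **Missing answers:** "If at least one question constituting the subscale is answered, the subscale should be tabulated without missing".

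SAP Section 8.5.2 (12) 2) applies this key: "Scores by subscale should be calculated using a scoring method (Section 4.16"). The subscale scores then go into descriptive statistics, paired t-tests of change from the first day of treatment, and MMRM estimates of that change. The errata of 26 March 2019 correct several other parts of the SAP but not Section 4.16.

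**The concern.** Two three-item subscales drawn from six items would be expected to use each item once. Here 13F contributes to both and 13E to neither, although Step 1 takes the trouble to score it. Nothing in the SAP explains a shared item. Because Section 8.5.2 sends the analyst to this table, anyone who follows the SAP as printed will compute at least one subscale from an item list that does not fit the rest of the table. Up to two KDQOL subscales are at stake, within the protocol's other endpoints.

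**Working it through.** **1. Item counts.** Each of the two rows agrees with its own stated count (3 and 3). The fault shows only when they are put side by side.

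| | A | B | C | D | E | F |
|---|---|---|---|---|---|---|
| Scored in Step 1 | yes | yes | yes | yes | yes | yes |
| Cognitive function | | yes | | yes | | yes |
| Relationship with people | yes | | yes | | | yes |
| Times used | 1 | 1 | 1 | 1 | 0 | 2 |

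The two rows have 3 + 3 = 6 places but hold only 5 distinct items.

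**2. The rest of the table.** Listing every item across all 19 subscales gives:

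- Item 13F is the only one used twice.
- The scored items used in no subscale are 13E and Questions 2 and 22. The last two are stand-alone questions, so 13E is the only lettered sub-item left out.
- Question 9 is the nearest comparison, since it too is split between two subscales. Vitality takes A, E, G, I and Mental health takes B, C, D, F, H: 4 + 5 = 9 items, each used once.
- The Symptoms row gives 12 items for Question 14 A–K plus L or M. That fits if L and M are alternatives (11 + 1 = 12) and has no bearing here.

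**3. Which row.** Changing one letter in either row removes the overlap: B, D, F with A, C, E, or B, D, E with A, C, F. The first gives a regular alternation, which makes Relationship with people the likelier faulty row. With that change, no item in the table is duplicated and only Questions 2 and 22 remain outside a subscale.

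**4. Effect on a subject's score.** With all items answered, each has weight 1/3:

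- printed score − expected score = (A + C + F)/3 − (A + C + E)/3 = (13F − 13E)/3
- one answer step between F and E: 20/3 = 6.7 points
- opposite ends of the scale: (100 − 0)/3 = 33.3 points

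If Cognitive function were the faulty row instead, the same formula would apply to that subscale.

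**5. Effect on change from the first day.** The error in a change score is (change in 13F − change in 13E)/3.

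- A subject with 13F = 80 and 13E = 40 at both visits is off by (80 − 40)/3 = 13.3 in level at each visit, and by 0 in change.
- If 13F moves from 60 to 80 while 13E does not move, the change is off by 20/3 = 6.7.

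SAP 8.5.4.1 also enters the first-day value as a covariate in the MMRM, so a level error at the first day reaches the model by that route. The documents give no KDQOL data from which to size this.

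**6. Missing answers.** As printed, a subject who answers only 13F receives the same score on both subscales, and one who answers only 13E is missing on both.

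**The case against.** The strongest reply is that the documents show an inconsistency but not which row is at fault. Neither the questionnaire wording nor the manual cited as SAP reference 2 is available, and the SAP never states that each item must be used once. Questions 2 and 22 are also scored without feeding a subscale, so an unused item alone proves little. This stands as far as it goes: the faulty row is an inference. The double use of 13F is the real anomaly, and the clean split of Question 9 tells against a deliberate overlap.

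A second reply is that the finding rests on one letter in a document translated from Japanese, so the slip may never have been in the source plan or the program. That is possible, but nothing in the text shows it, and the errata leave the section as it is. Section 4.16 has other copying faults: its text points to Tables 7.5.3.2 and 4-1, which are not the numbers its own tables carry. These fit a transcription slip but do not show where it arose.

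A reader might go further than the documents allow in three ways:

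- **That the subscale measures a different construct.** On the likely reading, two of its three items are right.
- **That the trial's results are biased by 6.7 to 33.3 points.** Those are level shifts for single subjects. The planned tests are of change, where a stable gap between F and E cancels.
- **That the shared item damages the analysis by correlating the two subscales.** It does induce correlation, but no planned KDQOL analysis relates one subscale to another.

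**Conclusion.** The point holds as an internal contradiction in the scoring key. Table 4.16.2 uses 13F twice and omits 13E, so at least one of the two Question 13 rows is wrong as written. Relationship with people is the likelier one, on the assumption that the two subscales are meant to divide the six items between them. On that reading one third of the 0–100 subscale comes from the wrong item, with the level and change errors derived above. Those figures assume that A, C, E and F are all answered; with A or C missing, the averaging rule gives the disputed item more weight.

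A reader might conclude that the KDQOL results were in fact computed wrongly. The documents do not support that, because they do not show which items the analysis program used. The haemoglobin endpoints, the safety analyses and the sample size do not depend on this table. It should still be corrected, because it is a scoring rule the analysis is told to follow.

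**What to change.** 1. Check both Question 13 rows of Table 4.16.2 against the manual cited as SAP reference 2. Check the Step 1 response direction of 13E at the same time: 13E now feeds no score, so a wrong direction would not have shown.
2. Correct the table by erratum. The expected entry for Relationship with people is Question 13 A, C, E, subject to the manual.
3. Check which items the analysis program used. SAP version 2 is marked final and its errata already describe Correction cohort analyses as not conducted, so a check limited to future programming would not be enough.
4. If the program used 13F for Relationship with people, rerun that subscale's descriptive statistics, paired t-tests and MMRM. If the manual shows that Cognitive function is the faulty row, do the same there.

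The cost is one erratum and, if needed, a line of scoring code and a rerun of one subscale's tables. No new data are required.
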